4) Subject safety and monitoring during gait testing: During the treadmill walking, stroke subjects will wear a harness suspended from the ceiling (no body-weight support) for safety. In addition, if needed, the stroke subjects will be allowed to hold on to the hand rails during walking. Heart rate, Borg rate of perceived exertion, and blood pressure will be recorded at baseline. Additionally, heart rate will be monitored throughout the session with a heart rate sensor that is placed on the chest under clothing (Polar USA, Lake Success, NY). If heart rate exceeds 80% of the age predicted heart rate maximum, walking will be stopped until it returns to baseline. In addition, blood pressure will be monitored at each rest break. If a subject's blood pressure exceeds 190/100 mmHg, the session will be stopped and their blood pressure will be continually monitored until it returns to baseline. We may also measure skin resistance using a small sensor wrapped around the finger. Subject's rating of perceived exertion on the Borg Scale of Perceived Exertion will also be monitored intermittently throughout the session. If a subject reaches level 16 on the Borg scale or appear too tired, they will be given a rest break⁶⁷.

5) Procedures for Motion Analysis:

As stated above, retro-reflective markers will be attached to the subjects' lower extremities^{68, 69}. Elastic bands (Fabrifoam, USA) will be wrapped around the thighs, calves and pelvis to which small, thermoplastic shells containing reflective markers will be attached. Additional markers will be taped to the subjects' shoes and on the upper back, shoulder, hip, knee, and ankle joints with adhesive skin tape. Marker data will be collected using a 7-camera motion analyses system (Vicon, Oxford, UK). We may also attach non-reflective adhesive markers to a few anatomical locations. During treadmill walking, ground reaction forces during treadmill walking will be collected using a treadmill instrumented with two 6-component force platforms under each belt (Bertec, USA). During over ground walking, ground reaction forces will be collected using a force plate embedded within the lab floor (AMTI, USA). In addition, in order to record muscle activity, small electromyography (EMG) sensors may be attached to various muscles. The EMG sensors will be attached using hypo-allergenic adhesive. EMG signals may be recorded from the following muscles: tibialis anterior, soleus, gastrocnemius,

quadriceps femoris, hamstrings, gluteus medius, and erector spinae. All analog data (force platform, EMG, footswitch, and stimulation channels) will be collected at 2400-Hz.

In addition to the walking trials described above, motion analysis data may be collected during 1- to 10-second long static postures (standing and sitting). During treadmill walking, subjects will wear a ceiling-mounted safety harness during all trials. An emergency shut-off switch will be positioned within arm's reach of the experimenter and can be used at any time by the experimenter to stop the treadmill. Subjects will be allowed rest breaks as often as requested. Similar to the described above, subjects' heart rate, perceived exertion, and blood pressure will be monitored during the session.

Risks

Risks associated with clinical testing, gait training, and motion analyses include falling, fatigue, poor heart rate and blood pressure response to walking and minor skin irritation from the adhesive tape. To minimize risk, subjects will wear a safety harness during the treadmill testing and will be given a rest break whenever requested. Heart rate will be monitored continuously and blood pressure will be monitored at rest breaks. Throughout the experiment, the experimenter has access to an emergency safety switch that can be used to stop the treadmill immediately.

*Risks associated with gait biofeedback:* The safety, feasibility, and effects of AGRF biofeedback have been evaluated in able-bodied and post-stroke individuals^{39, 66}. Here, we evaluate the short-term effects of a short, 2 to 6-minute AGRF biofeedback bouts with different biofeedback interfaces. The speed ranges (SS and Fast) and AGRF ranges (AGRFmin and AGRFmax) will be planned using each individual's own baseline walking data, making them customized to their own walking capacity. Potential risks during biofeedback bout training may be similar to those encountered during strenuous exercise – tiredness, muscle fatigue, muscle soreness, and potential for joint discomfort. Potential risks from the VR versions of the game include dizziness, nausea, and sense of disorientation.

Potential Benefits

These procedures are experimental, and the responses of individual subjects to the gait training sessions may vary widely. We do not anticipate that the participants will gain any benefits from study participation. The long-term findings of this study can help us better understand the effects of and guide the design of clinical gait rehabilitation which can benefit other stroke survivors in the future.

Type of Information Collected

During clinical testing, to help characterize the clinical characteristics of the subject group, information such as age, time since the stroke, height, weight, side of hemiparesis, etc. will be collected. To help characterize the level of impairment of the subject group, information such as walking speed, endurance, walking function score, lower extremity sensation, etc. will be collected. During motion analysis and gait training, the 3-dimensional camera system will be used to track the 3-D positions of the subject's segments; these data will be used to compute joint angles, ground reaction forces, joint moments, joint powers, etc. All subject data will be de-identified and then compiled on an excel spreadsheet and imported into SPSS 21 (SPSS,

Chicago, IL) for statistical analysis. De-identified data will be disseminated through group discussions, presentations and publications.

Management of Subject Data

Subjects will not be anonymous to the researchers. As a first step during data management, subject identities will be de-identified by assigning each subject a number. Any computer files containing information that link the identifiable subject data with the de-identified subject number will be password protected and stored on a secure Emory University computer. Only de-identified data will be used to compile spreadsheets of the various outcome measures collected as part of this study (joint angles, clinical impairment scores, EMG, etc.). De-identified data may be stored for future use until 5-years after completion of the study. All signed consent forms will be stored in the subject's folder (organized by de-identified subject numbers) in a locked file cabinet at the University. Participants will not be audiotaped, photographed or videotaped without their permission during this study.

6. Participant selection

For Aim 1 and 2, for preliminary testing of the game design and to get user-feedback on game usability, we plan to collect user-survey and feedback data on 10 stroke survivors and 10 ablebodied individuals. For Aim 3, which is the clinical trial portion of the project, we plan to collect data on a sample of 12 individuals post-stroke and 8 able-bodied neurorehabilitation clinicians.

Inclusion Criteria for Post-Stroke Subjects are: 1) age 30-90 years, 2) chronic stroke (>6 months post stroke) affecting the left leg, 3) ambulatory with or without the use of a cane or walker, 4) able to walk for 2 minutes at the self-selected speed without an orthoses, 5) resting heart rate 40-100 beats per minute.

Exclusion Criteria for Post-Stroke Subjects are: 1) cerebellar signs (ataxic ("drunken") gait or decreased coordination during rapid alternating hand or foot movements, 2) history of lower extremity joint replacement, 3) inability to communicate with investigators, 4) neglect/hemianopia, or unexplained dizziness in last 6 months, 5) neurologic conditions other than stroke, 6) orthopedic problems in the lower limbs or spine (or other medical conditions) that limit walking or cause pain during walking.

Inclusion Criteria for Able-Bodied Individuals are: 1) age 18 to 90 years, 2) no history of neurologic disease, 3) no history of orthopedic disease or injury affecting the lower extremity.

Exclusion Criteria for Able-Bodied Individuals are: 1) history of neurologic disease, 2) history of orthopedic disease or injury to the lower extremity in the past 6 months, 3) pain or discomfort during walking, 4) cardiovascular or medical condition affecting ability to exercise or walk.

Subject Recruitment. Study participants will be recruited from the general community within and outside Emory University.

Withdrawal from study. Participation in the present study will be voluntary and subjects will be able to opt out of the study at any time.

Inclusion of children: Our subject population will be representative of adults with stroke and healthy adults. The incidence of stroke is considered rare in children, estimated to be less than 13 cases per 100,000 children⁷⁰ and their inclusion would not provide additional information compared with the data gathered in adults.

7. Statistical analysis

Hypotheses testing will be done with a p-value set at 0.05. The primary biomechanical outcome variables will be peak AGRF and trailing limb angle. Secondary variables will be user self-reports regarding game engagement, motivation, and fatigue.

Power Analysis: The current protocol is designed as a preliminary study, and will be used to conduct systematic power analysis, effect-size and sample-size calculation, which will be utilized to design a larger-scale future study.

8. Adverse event reporting

We will record and notify the IRB of any adverse events that occur during the protocol.

10. Device information

Equipment for Motion Analysis and Gait Retraining: A 7-camera system will be used to collect motion analysis data (Vicon, Oxford, UK). Ground reaction forces during treadmill walking will be collected using a treadmill instrumented with two 6-component force platforms under each belt (Bertec, USA). During over ground walking, ground reaction forces will be collected using a force plate embedded within the lab floor (AMTI, USA). In addition, small electromyography (EMG) sensors will be attached to various muscles to collect EMG data (Noraxon Inc., Arizona, USA). The EMG sensors will be attached using hypo-allergenic adhesive. Pressure-sensitive foot switches (25-mm diameter MA-153, Motion Lab Systems, LA) will be attached to the underside of the subjects' shoes; the foot switch data will be used to record gait events (Noraxon Inc, Arizona, USA). All these devices widely used for measurement of human movements.

Equipment for gait biofeedback: The auditory and visual biofeedback will be provided using a visual display projector screen and a speaker pointed toward the participant. The visual feedback display comprises a horizontal line graph with a moveable cursor that represents the current measured value of antero-posterior ground reaction force for the right leg. The biofeedback software is a plugin provided by The MotionMonitor, Innovative Sports Training Inc., Illinois, USA. The game-based biofeedback interfaced will be designed and developed as part of this current project, with help from our collaborators at Savannah College of Arts and Design (SCAD) and Georgia Institute of Technology. We may use a commercial off-the-shelf VR headset such as the Oculus for the VR display.

11. References

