Aim 3. To obtain user data from stroke survivors and neuro-rehabilitation clinicians reqarding our newly developed real-time AGRF biofeedback gait training game. Drs. [name] and [name], stroke gait rehabilitation experts at Emory University will complete this aim. The game will be tested on 12 individuals with chronic post-stroke hemiparesis and 5 neuro-rehabilitation clinicians. Participants will complete 1-2 sessions comprising exposure to 2-3 gait biofeedback systems: (i) newly developed game-based interface (projector screen display), (ii) traditional, non-game interface, and (iii) VR version of the game (head-mounted display). Outcomes will include measures of participant engagement, user-reports and survey-responses on motivation, gait performance, fatigue, game characteristics, and adverse effects (e.g. nausea, dizziness) during game exposure.

Study Hypotheses

Aims 1 and 2 are focused on design and development of the gait biofeedback gaming interface. Aim 3 is a small-sample clinical trial evaluating the newly development biofeedback game. For Aim 3, we *hypothesize* that compared to the traditional non-game biofeedback, game-based biofeedback will induce greater improvements in paretic leg biomechanics, improve participant motivation and engagement, reduce fatigue, without significant adverse effects.

5. Study design and methods

Our 2-year project comprises aims related to the design and development phase (aims 1 and 2) and testing phase (aim 3) for an innovative, game-based, gait biofeedback system. The overview, timeline, and potential future directions for the proposal are provided in Figure 4.

The study will comprise 2 phases:

[figure not shown]
Phase 1 will include the design and development of the game. For study phase 1, the P.I. will work with collaborators at Savannah College of Art and Design (SCAD) and Georgia Institute of Technology to develop the software interface (visual display and graphics) and the hardware instrumentation for the gait biofeedback game system. During the later stage of phase 1, preliminary feedback about the game design will be obtained from 10 stroke survivors and 5 able-bodied individuals.

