Methods for evaluation on stroke survivors: The newly developed games will be tested on 12 individuals with chronic post-stroke hemiparesis and 12 able-bodied adults. Inclusion criteria for stroke participants will include \geq 6-months elapsed since a cortical or subcortical stroke, ability to walk on a treadmill for \geq 2-minutes, ability to communicate with study team, stroke affecting the right leg (to match control participants' biofeedback targeted leg and due to constraints with the game design prototype). Exclusion criteria include orthopedic or neurological conditions preventing walking, neurologic diagnosis other than stroke, cerebellar signs, and cognitive impairments preventing communication during the experiment⁶². Inclusion criteria for able-bodied will be ability to walk, and absence of orthopedic, neurological, or medical conditions that limit walking. Our proposed sample size is based on our studies (N=7 stroke, N=7 able-bodied) where we detected significant increase in targeted leg peak AGRF with power \geq 0.80, with additional participants included to account for the self-report and survey-based game-evaluation outcomes.

Study participants will complete one session comprising exposure to gait biofeedback systems in an order determined by block randomization (3 blocks). Participants will be exposed to 2-3 types of biofeedback interfaces – (i) the AGRF biofeedback game (projector-display, non-VR), and the (ii) traditional, non-game-based, interface (currently used, shown in Figure 2). If we cannot test all 3 gait feedback conditions in 1 session, participants may be asked to complete a 2nd experimental session when 2-3 feedback conditions (and control walk) will be evaluated. In a separate session, some

Outcome variables for Aim 3		
Participant engagement during biofeedback	Hopkins rehabilitation engagement rating scale Pittsburgh rehabilitation participation scale	
Motivation, boredom, and fatigue	10-point visual analog scale Open-ended, non-leading survey questions	
Successful completion of targeted training task	Evaluate success rate (%steps for which target paretic AGRF was achieved)	
Feedback about user experience and game (game ease-of-use, game aesthetics, challenge, ability to understand the game instructions)	10-point scale self-reports Open-ended, non-leading survey questions	
Adverse effects or events	Nausea, dizziness, other negative responses	

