participants may complete preliminary or exploratory testing of the VR version of the biofeedback game (head-mounted AR or VR display), which will be used to determine feasibility and preliminary effects of VR-based feedback on gait. The participants will be exposed to each of the 2 types of biofeedback for a matched duration (2 to 6-minutes). Kinematic and GRF data will be collected as participants walk on a

split-belt instrumented treadmill at a self-selected speed. Consistent with our preliminary stroke biofeedback studies, target AGRF will be calculated as 10-20% above the *paretic AGRF*. The same % target value for paretic AGRF will be used for all 3 types of biofeedback (i.e. similar challenge level). At the start of each walking task, participants will be provided scripted, verbal instructions regarding the training task (i.e. generate greater push-off force with the paretic leg) and the biofeedback interface (i.e. how the game works). Participant will be told to complete the biofeedback task for as many minutes as possible without a break. Participants can request a break during the biofeedback, as needed. During and after completion of the gait evaluation session, we may obtain outcomes as listed in the table. To assess participant engagement during each biofeedback bout, we may use 2 published scales – the Hopkins Rehabilitation Engagement Rating Scale ⁶³ and the Pittsburgh rehabilitation participation scale ⁶⁴. We will also ask the participant to self-report on how much fatigue and engagement they felt while walking with each feedback interface, using a Likert scale, a user-experience questionnaire, and/or a NASA-task load index (NASA-TLX) scale. Qualitative comments or feedback will also be gathered. Sex and age as biological variables may influence these outcomes, and will be addressed in our study design.

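### Absence of significant adverse effects is part of the Aim 3 hypothesis, but 12 stroke participants cannot support it, whether the word is meant statistically or clinically

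*Combined protocol and SAP*

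**What the plan says.** Section 4 (Study Hypotheses) states a comparative hypothesis for Aim 3: "compared to the traditional non-game biofeedback, game-based biofeedback will induce greater improvements in paretic leg biomechanics". The same sentence adds gains in motivation and engagement, and ends with "reduce fatigue, without significant adverse effects". 

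Section 7 supplies the only decision rule: "Hypotheses testing will be done with a p-value set at 0.05". It names peak AGRF and trailing limb angle as primary, and self-reported engagement, motivation and fatigue as secondary. Adverse effects appear in neither list.

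The outcome table for Aim 3 in Section 5 lists adverse effects as "Nausea, dizziness, other negative responses", with no scale, threshold or analysis. Nowhere is there a definition of significant, a tolerable rate, a margin or a confidence interval for them.

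On numbers, Section 4 says: "The game will be tested on 12 individuals with chronic post-stroke hemiparesis". Section 6 also gives 12 people post-stroke for Aim 3. Each person meets both main interfaces for a matched duration (Section 5, Aim 3 methods), so the data are paired. The headset is for a subset: in a separate session some "participants may complete preliminary or exploratory testing of the VR version of the biofeedback game". The Risks part of Section 5 names dizziness, nausea and disorientation as possible effects of the VR version, without an expected rate.

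**The concern.** The other parts of the hypothesis need evidence of a difference. The adverse-effect part is met by not finding one, so the smaller the sample, the easier it is to confirm. The plan gives no criterion that would prevent this. If the word is statistical, a non-significant comparison in 12 people could be taken as support. If it is clinical, no threshold is given, and no limit is put on the rate that 12 exposures can exclude.

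At stake is a report that the game or the headset had no significant adverse effects when the data are compatible with nausea or dizziness being common. Section 7 says this study will feed the design of a larger one, so an unqualified statement could be carried forward. The headset, whose risks the protocol names, may have the fewest users.

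**Working it through.** **The plan's own figure.** None is given for adverse effects. The sample-size statement (Section 5, Aim 3 methods) reports power of at least 0.80 for peak AGRF in earlier studies with 7 stroke and 7 able-bodied participants. It gives no effect size or SD, so it cannot be reproduced. For a two-sided 0.05 paired t-test, 80% power needs a standardised effect of 1.27 at N=7 and 0.89 at N=12. This has no bearing on adverse effects.

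**Inputs.** n = 12 stroke participants, each with both interfaces (Sections 4, 5 and 6); alpha 0.05 (Section 7). Assumptions: each effect is recorded as yes or no for each interface, and nobody is unwell on the non-game interface. Test and sidedness are unstated, so several are shown.

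**Reading 1: the 0.05 rule is applied.** Let b people be unwell on the game only and none on the non-game interface only.
- Exact two-sided McNemar: p = 2 × 0.5^b.
- Exact one-sided, and two-sided mid-p: p = 0.5^b.
- Uncorrected McNemar chi-square: b²/b = b on 1 df.
- Fisher, ignoring the pairing: b of 12 against 0 of 12.

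| Test | Largest non-significant b | p there | p at b + 1 |
|---|---|---|---|
| Exact two-sided McNemar | 5 of 12 (42%) | 0.0625 | 0.031 |
| Continuity-corrected McNemar | 5 of 12 (42%) | 0.074 | 0.041 |
| Exact one-sided, or mid-p | 4 of 12 (33%) | 0.0625 | 0.031 |
| Fisher (unpaired) | 4 of 12 (33%) | 0.093 | 0.037 |
| Uncorrected chi-square | 3 of 12 (25%) | 0.083 | 0.0455 |

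The zero-event assumption is favourable to detecting harm. With one person unwell only on the non-game interface, 7 against 1 is still non-significant (exact two-sided p = 0.070).

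The chance of significance with the exact two-sided test is P(X ≥ 6), X ~ Bin(12, π), where π is the true share unwell on the game only: 5.4% at π = 25% and 33.5% at π = 40%. For the one-sided test the figures are 1 − 0.842 = 15.8% and 1 − 0.438 = 56.2%. The documents give no rate; these values of π are illustrative.

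**Reading 2: the result is read descriptively.** With 0 of n affected, the upper 95% limit is 1 − 0.025^(1/n) two-sided (Clopper-Pearson) and 1 − 0.05^(1/n) one-sided.
- n = 12: 1 − 0.025^(1/12) = 26.5%; one-sided 22.1%.
- One event in 12 raises the two-sided limit to 38.5%.

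**Headset.** The number of users is not given, so a range is needed. With 0 affected, the two-sided limit is 1 − 0.025^(1/5) = 52% for n = 5, 1 − 0.025^(1/8) = 37% for n = 8, and 26.5% if all 12 take part. On the test reading, 5 of 5 affected on the headset and none on the non-game interface gives 2 × 0.5^5 = 0.0625, still non-significant.

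**Able-bodied participants.** The Aim 3 methods give 12; other parts of Sections 5 and 6 give different numbers. Pooling 12 with the 12 stroke participants would leave 5 against 0 at p = 0.0625 (5/24 = 21%), and 0 of 24 would have an upper limit of 1 − 0.025^(1/24) = 14%. That is not a rate for stroke survivors.

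**The case against.** A reader might infer that the plan sets a significance test for adverse effects and will declare the game safe if p exceeds 0.05. The documents do not support that. Section 7 leaves adverse effects out of both its lists. Elsewhere they are handled by recording (Section 5, gait-analysis step ix) and by notification to the IRB (Section 8). The test reading comes only from joining a phrase in Section 4 to a general alpha statement in Section 7. The word significant, in ordinary use, may simply mean important.

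Nor does the plan draw a no-harm conclusion. A hypothesis is not a conclusion, and the protocol calls the work preliminary and small-sample and names the headset risks openly. McNemar's test is not specified, and Section 4 ties adverse effects to exposure to the game, so a paired yes/no record for the non-game interface is not clearly planned. Finally, Section 7 names no test for any outcome, so this gap is part of a wider one.

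All of that stands, and it makes the test-based figures conditional. It does not remove the point. The clinical reading has no criterion either, and the limit of 26.5% for 0 of 12 depends on no test. Preliminary status excuses low power, but not a hypothesis that low power helps to confirm.

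**Conclusion.** The point holds in a conditional form. The adverse-effect part of the Aim 3 hypothesis has no defined meaning and no analysis, and on neither reading can 12 stroke participants support absence of harm. If the 0.05 rule is used, 3 to 5 of 12 people (25% to 42%) could be unwell on the game only without significance. This assumes paired yes/no data and no events on the other interface, and the count depends on the unstated test and sidedness. If the result is read descriptively, even a perfect record leaves rates up to 26.5% open (22.1% one-sided), and up to about 52% if only 5 people use the headset, a number that is assumed. Able-bodied participants add exposure but not a stroke-specific rate. The primary biomechanical analysis is not affected. This is a cheap improvement to the safety wording and reporting.

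**What to change.** In Sections 4 and 7, take the adverse-effect clause out of the hypothesis and replace it with a descriptive safety objective. State that:
- the number and percentage of stroke participants with each adverse effect will be reported separately for the traditional, projector-game and head-mounted interfaces, using the number exposed to each as the denominator;
- each percentage will carry Clopper-Pearson 95% limits;
- safety will not be inferred from p > 0.05, and the conclusion will go no further than the rates that the upper limit excludes (with 0 of 12, rates above 26.5%);
- able-bodied participants will be shown separately.

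The cost is wording and a little record-keeping: each effect must be attributed to the bout in which it occurred. No extra participants or sessions are needed. The drawback for the investigators is a less favourable safety statement.

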- (ix) Collection of self-report data regarding engagement, adverse effects, challenge, muscle soreness/fatigue during biofeedback: In order to evaluate the feasibility and subject perceptions in response to biofeedback training, we may ask the participant to rate their engagement or motivation, level of challenge encountered during biofeedback, and amount of fatigue on a 0 to 10 visual analog scale. Any other feedback, comments, and adverse effects reported by the subject will also be recorded.
- 3) **Procedures for gait biofeedback:** During biofeedback, auditory and visual biofeedback will be provided using a visual display screen and a speaker pointed

toward the participant. The visual feedback display will vary according to the type of biofeedback interface being evaluated. For the traditional non-game biofeedback, the visual display comprises a horizontal line graph with a moveable cursor that represents the current measured value of antero-posterior ground reaction force for the targeted leg (The MotionMonitor, Innovative Sports Training Inc., Illinois, USA). The targeted peak AGRF range appears as a target line with vertical bars on either end, representing a 6-Newton error-tolerance range centered around the target AGRF³⁹. The auditory feedback comprises an audible "beep" produced every time the cursor entered the target range, i.e. the participant achieves the targeted peak GRF value during their gait cycle^{39, 66}. This same AGRF biofeedback audio-visual system has been successfully used in previous studies in both able-bodied and stroke survivors, showing the feasibility of the biofeedback setup^{39, 66}. For game-based biofeedback, the newly-developed game-based interfaces will be used. The game-based biofeedback may be displayed on a projected screen or with VR goggles.

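### Nausea and dizziness are named Aim 3 outcomes but have no rating scale, no pre-bout value and no required recording by bout, so few or no recorded events would be weak evidence

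*Combined protocol and SAP*

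**What the plan says.** Under Study Hypotheses (section 4), the Aim 3 hypothesis opens with a comparison: "compared to the traditional non-game biofeedback, game-based biofeedback will induce greater improvements in paretic leg biomechanics". The same sentence ends with the expectation that the game will "reduce fatigue, without significant adverse effects".

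Adverse effects then appear in four places:

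- **Aim 3 summary (section 4):** user reports and survey responses are to cover several topics, the last being "adverse effects (e.g. nausea, dizziness) during game exposure".
- **Aim 3 outcome table (section 5):** the adverse-effects row reads "Nausea, dizziness, other negative responses". It gives no scale, time point or interface. On timing and commitment, the text says "During and after completion of the gait evaluation session, we may obtain outcomes as listed in the table".
- **Step (ix), gait analysis procedures:** the heading is "Collection of self-report data regarding engagement, adverse effects, challenge, muscle soreness/fatigue during biofeedback". The text offers a 0 to 10 visual analog scale for engagement or motivation, challenge and fatigue. For symptoms it says: "Any other feedback, comments, and adverse effects reported by the subject will also be recorded".
- **Section 8:** any adverse event during the protocol is recorded and notified to the IRB.

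Elsewhere, step (viii) allows gait biomechanics before, during and after each bout, and optional self-reports of exertion, engagement and fatigue per bout. The safety-monitoring procedures take heart rate, perceived exertion and blood pressure at baseline. Section 7 lists adverse effects as neither primary nor secondary and gives no analysis for them.

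**The concern.** The hypothesis includes a safety clause and the plan names the symptoms that matter, yet these are the items left without an instrument. Engagement and fatigue get a number; nausea and dizziness get a note if the participant mentions them. Two problems follow.

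First, a mild symptom that nobody asks about may go unrecorded. Any such loss pushes the result towards a clean record, which is the result the hypothesis hopes for.

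Second, without a value before the bout, a symptom seen after it cannot be attributed in that person. It may have been present on arrival: the stroke exclusion covers only "unexplained dizziness in last 6 months". It may come from the treadmill walking that precedes the bouts, or from the previous bout.

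The study is meant to inform a larger trial, so what is at stake is whether it yields symptom data that can be used.

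**Working it through.** **1. Is there a plan figure to reproduce?** No. The protocol gives no expected symptom rate, margin or power for adverse effects. Its sample size argument concerns peak AGRF only.

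**2. Where could a symptom value come from?**

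| Place | What is captured | Nausea or dizziness? |
|---|---|---|
| Safety monitoring, baseline | heart rate, perceived exertion, blood pressure | no |
| Step (viii), before a bout | gait biomechanics | no |
| Step (viii), per bout (optional) | exertion, engagement, fatigue | no |
| Step (ix), 0 to 10 scale (optional) | engagement or motivation, challenge, fatigue | no |
| Step (ix), free recording | what the subject reports | yes; no scale, bout or baseline |
| Aim 3 outcome table (optional) | symptoms named | yes; no scale, bout or baseline |

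No row gives a rated value, a pre-bout value or a required link to the interface.

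**3. How much walking comes before the bouts?** The text of step (vi) allows 5 to 10 calibration trials of 30 to 120 seconds, that is 5 × 30 s = 2.5 minutes up to 10 × 120 s = 20 minutes. The speed-finding and baseline trials of steps (iii) and (iv) come on top. Each biofeedback bout lasts 2 to 6 minutes. Background symptoms from walking are therefore plausible.

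**4. What would a record of no events be worth?** Let n = 12 (stroke participants), p = true probability that a participant has symptoms with the game, and s = share of symptomatic participants whose symptom is recorded. Both p and s are assumptions, because the documents give neither. The chance of recording none is (1 − p·s)^12.

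| p | s = 1 | s = 0.5 | s = 0.25 |
|---|---|---|---|
| 10% | 0.90^12 = 28.2% | 0.95^12 = 54.0% | 0.975^12 = 73.8% |
| 20% | 0.80^12 = 6.9% | 0.90^12 = 28.2% | 0.95^12 = 54.0% |
| 30% | 0.70^12 = 1.4% | 0.85^12 = 14.2% | 0.925^12 = 39.2% |

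At p = 20%, moving from full capture to one quarter turns an empty record from unlikely (6.9%) into slightly more likely than not (54.0%).

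**5. What can be learned with full capture?** With zero events in n people, the one-sided 95% upper limit is 1 − 0.05^(1/n). For n = 12 this is 22.1% (two-sided exact limit, 1 − 0.025^(1/12) = 26.5%). For a paired comparison of interfaces, an exact two-sided McNemar test reaches 0.05 only with at least 6 discordant participants all in the same direction: 2 × 0.5^6 = 0.031, against 2 × 0.5^5 = 0.063 for five. With symptoms under the game only in 30% of participants and never under the traditional interface only (assumed), power at n = 12 is 11.8%. Better recording makes the contrast estimable but leaves it imprecise.

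**The case against.** A reader might infer more than the documents support, in four ways.

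- **That symptoms are collected for the game only.** Only the Aim 3 summary is worded that way. The outcome table, the heading of step (ix), which refers to biofeedback in general, and section 8 carry no such limit. What stands is an inconsistency in the summary.
- **That capture is certainly unprompted.** The Aim 3 summary mentions survey responses, and the step (ix) heading describes self-report data on adverse effects, so some asking may be intended. What stands is that no question, scale or firm commitment is written down.
- **That the protocol claims the game adds no nausea or dizziness over the traditional interface.** It does not. The safety clause sits in a comparative sentence but can be read as absolute, and it names no symptom. An absolute reading would still need systematic elicitation.
- **That the comparison cannot be measured.** This is too strong. Each participant meets both interfaces, in randomized order and for matched time. The calibration walking precedes both bouts, so background is balanced on average. Events could be counted by interface if the bout were noted. What stands is that the plan does not require the bout to be noted, and that balance on average does not resolve attribution in one person or reassure much in 12.

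There are also points on proportion. The Risks section places dizziness, nausea and disorientation with the VR versions, which are exploratory and for some participants only. The study is preliminary. A physical therapist, rest breaks and physiological monitoring protect participants meanwhile. The under-reporting share is assumed, not documented. All of this is fair and keeps the point modest, but none of it supplies the missing measurement.

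**Conclusion.** The concern holds in limited form. Nausea and dizziness are named outcomes behind a stated safety expectation, but the plan specifies no scale, no pre-bout value and no required recording by bout. A finding of few or no events would be weak evidence under either reading of the hypothesis. At an assumed true probability of 20% in 12 stroke participants, an empty record has a chance of 6.9% to 54.0%, depending on whether all or a quarter of cases are recorded. The absence of an instrument follows from the text alone; the percentages rest on assumed rates and shares.

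This should be changed because it is cheap, not because it threatens the primary biomechanical outcomes. Sample size is a separate limit that the change does not remove, so the symptom results should be descriptive.

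**What to change.** - **Step (ix):** ask every participant to rate nausea, dizziness and disorientation on the existing 0 to 10 scale once immediately before and once immediately after each bout: game, traditional, control walk and, where used, VR. Make this a firm commitment. Continue to record volunteered events, and log each against its bout.
- **Reporting:** give the pre-to-post change for each interface and the game-minus-traditional difference descriptively. State what counts as an event and give exact intervals for event rates. Do not frame it as a significance test.
- **Aim 3 summary:** replace the restriction to game exposure with wording that covers each interface, to agree with the outcome table, step (ix) and section 8.

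**Cost:** 3 items × 2 time points × 4 conditions = 24 short ratings per person at most, or 18 without VR. No equipment or extra participants are needed. Asking directly will raise reported symptom counts under all interfaces, which the report should say.
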